1.3 Research Design and Methods

A. Research Procedures

This study is a randomized controlled trial that will randomize participants to receive either an emotional appeal about a child with cancer who needs a bone marrow transplant or a rational appeal using data on the racial/ethnic disparities within the transplant registry. (See Appendix A for condition prompts).

Participants will be recruited through the Psychology Subject Pool through the SONA system which will then link students to the study measures in Qualtrics. Participants will be asked their age to confirm eligibility to participate (students must be between 18-35) and eligible students will be presented with the consent form in Qualtrics. Participants will then be asked to complete measures of demographic information, personality/psychological characteristics, and transplant-related knowledge, intentions, and attitudes. All participants will then be given background information on bone marrow transplants (See Appendix A for text).

Randomization: Students will be randomized by sex in Qualtrics to the emotional presentation condition or the rational presentation condition. The emotional condition will tell the story of a fictional pediatric patient with cancer who needs a transplant. The rational condition will describe the facts about the need for diversity in the registry (See Appendix A for condition prompts).

After being presented with the rational or emotional appeal, participants will again be asked their intentions to register, their motivations for registering, and their mood.

B. Data Points

Study data will include demographic information and responses to questionnaires given during the survey in Qualtrics.

C. Study Duration

Participation will last approximately 30 minutes.

D. Endpoints

The study will continue to collect data until a sufficient sample size is accrued.

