1.6 Study Variables

A. Independent Variables, Interventions, or Predictor Variables

The primary independent variable will be group (emotional or rational condition).

Emotional Appeal: Participants will be presented with a short vignette about a child undergoing cancer treatment and needing a bone marrow transplant in order to survive cancer. A publicly available animation of a teddy bear and hospital tools is also included in this condition.

Rational Appeal: Participants will be presented with data regarding the importance of considering race/ethnicity when looking for a bone marrow transplant donor and the likelihood of finding a match based on the patient's racial/ethnic background. An infographic depicting this information was created for this study.

Secondary Independent Variables: Additionally, demographic factors (race/ethnicity, sex, age), Altruism, Self-Esteem and Knowledge will be tested as secondary independent variables.

A full list of study measures is included in Appendix B.

Construct/Measure Name	Description
Demographics	(8) items will be used to assess the demographics of the student population.
Altruism	The Self-rated Altruism Scale (20 items) assesses altruistic behavior. Specifically, the questions refer to certain altruistic actions that students have partaken in and their frequency of said activities (Rushton, Chrisjohn, & Fekken, 1981).
Self-Esteem	The Rosenberg Self-Esteem Scale (10 items) tests the self-worth of an individual by testing the negative and positive feelings about ones' self using a 4-point Likert scale (Rosenberg, 1965).
Social Desirability	The Marlowe Crown Social Desirability Index short form (13 items) will be used to assess how much student responses are influenced by demand characteristics of participating in research (Fischer & Fick 1993).
Healthcare Distrust	The Healthcare Distrust Scale (10 items) assesses the level of trust participants have in the healthcare system. Specifically, the scale covers the positive and negative aspects of the healthcare system and how trust impacts choices (Rose et al., 2004).
Knowledge	This knowledge measure tests (12 items) misconceptions about the bone marrow registry and will be used to assess the general knowledge of the population we are administering the survey in to see the depth of knowledge regarding the research topic. This survey will also assesses opinions of participants regarding the process of going through a bone marrow transplant (Vasconellos 2011).

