4.0 Subject Considerations

4.1 Subject Selection and Enrollment Considerations

A. Method to Identify Potential Subjects

Potential subjects for the study will be identified by their current enrollment in Introduction to Psychology (50:830:101) or Method and Theory of Psychological Research (50:830:255).

B. Recruitment Details

The study will be posted to the Psychology Subject Pool which is hosted on the website SONA, maintained by the Psychology Department. Students are given the opportunity to participate in research as part of their class experience and receive class credit for participation. No additional recruitment will take place.

C. Subject Screening

Describe whether and how individuals will be screened for eligibility and by whom.

▪ **Inclusion Criteria**

Students enrolled Introduction to Psych (101) and Method and Theory (255) who are between the ages of 18-35 will be eligible to participate. Students will be asked to confirm that they are in the specified age range in Qualtrics before completing the informed consent form.

▪ **Exclusion Criteria**

Students under 18 years of age or over 36 or older will be excluded.

D. Privacy Protections

This study will not collect any identifiable participant data. Sona creates a unique randomly generated participant ID that is used in Qualtrics to collect data. The Sona system will separately maintain participant email addresses for the purpose of assigning class credit, but this will not be linked to the data collected in Qualtrics. When a student completes the survey in Qualtrics, they are returned to the Sona system so that they may receive class credit. Researchers will only identify data by the unique randomly generated participant ID.

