4.7 Risks of Harm/Potential for Benefits to Subjects

A. Description of Risks of Harm to Subjects

- **Reasonably Foreseeable Risks of Harm**

The foreseeable risks associated with participating in this study are due to the study content being related to cancer and other blood-based conditions. Participants may find it distressing to read about a child with cancer in need of a bone marrow transplant.

- **Risk of Harm from an Intervention on a Subject with an Existing Condition**

There are no documented risks to participation in this type of study.

- **Other Foreseeable Risks of Harm**

Participation will be kept confidential and anonymous. Researchers will not have access to study names or identifying information.

- **Observation and Sensitive Information**

N/A

B. Procedures which Risk Harm to Embryo, Fetus, and/or Pregnant Subjects

N/A

C. Risks of Harm to Non-Subjects

N/A

D. Assessment of Social Behavior Considerations

N/A

E. Minimizing Risks of Harm

Participants will be told the purpose of the study before consent, including that we are trying to learn about what motivates individuals to donate bone marrow/stem cells for patients with cancer and blood-based health conditions. Should they be uncomfortable with this study content they can elect not to participate. Further, should participants become uncomfortable while answering any questions or while reading about the reasons patients need a transplant, they can skip questions or stop participation at any time. Finally, participants will be provided with the principal investigator's contact information should they need to discuss the study content further.

- **Certificate of Confidentiality**

N/A

- **Provisions to Protect the Privacy Interests of Subjects**

N/A

F. Potential Direct Benefits to Subjects

There are no direct benefits for participating in the study, although their participation may help increase diverse enrollment in the NMDP in the future.

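### Section 1.3 A randomises by sex without naming the strata or covering a blank or other answer, and section 6.1 leaves the randomisation factor out of the appeal comparison

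*Combined protocol and SAP*

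**What the plan says.** **Allocation.** Section 1.3 A opens with the general intent: "This study is a randomized controlled trial that will randomize participants to receive either an emotional appeal about a child with cancer". It then gives the rule: "Students will be randomized by sex in Qualtrics to the emotional presentation condition or the rational presentation condition". It does not state the levels of sex, the ratio or the balancing method.

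**Order of events.** Sex is collected in the survey, after consent and before the appeal: "Participants will then be asked to complete measures of demographic information, personality/psychological characteristics, and transplant-related knowledge, intentions, and attitudes". Section 1.6 A groups sex with the other predictors: "demographic factors (race/ethnicity, sex, age), Altruism, Self-Esteem and Knowledge will be tested as secondary independent variables". The response options for the sex item are not in the text available here; section 1.9 A says the measures were uploaded separately as Appendix B.

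**Eligibility.** Section 4.1 C sets course enrolment and age only: "Students enrolled Introduction to Psych (101) and Method and Theory (255) who are between the ages of 18-35 will be eligible to participate". The check before consent covers age: "Students will be asked to confirm that they are in the specified age range in Qualtrics before completing the informed consent form".

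**Skipping.** Section 4.7 E says of participants who become uncomfortable that "they can skip questions or stop participation at any time". It exempts no survey item, and no section says the sex item must be answered.

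**Analysis.** Section 6.1 is one sentence naming analysis of variance and linear regression. It lists no model terms and does not mention the factor used in randomisation.

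**The concern.** There are two linked gaps.

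The first is that the allocation rule is incomplete. It depends on an answer that an eligible, consented student may leave blank or may give in a form that fits neither of the two usual categories. The rule does not say what happens then. The survey runs unattended on the student's own device in a single session (sections 1.9 A and 1.10), and researchers hold only a random ID (section 4.1 D). The protocol therefore describes no later point at which a missed allocation could be put right. At stake are the reproducibility of the allocation and the possible exclusion of eligible students from the appeal comparisons (Objectives 2 and 3, Hypotheses 3 to 5).

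The second gap is in the analysis. A factor used to restrict randomisation belongs in the model for the treatment comparison. Here it appears only as a secondary predictor, although section 1.2 cites work in which women were readier to register (while noting that this is not consistent across studies).

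**Working it through.** **Step 1. Can a student reach randomisation without a male or female answer?** Set the sections side by side:

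| Question | Section | Answer |
|---|---|---|
| Is sex needed to enter? | 1.3 A, 4.1 C | No: course and age only |
| When is it asked? | 1.3 A | After consent, before the appeal |
| Must it be answered? | 4.7 E | Not stated; skipping is allowed to those who become uncomfortable |
| Which strata exist? | 1.3 A | Not stated |
| What happens to a blank or other answer? | none | Not stated |

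The text does not rule such a student out and gives no rule for allocating one.

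**Step 2. How many students?** The documents give no rate, so it is assumed. Students affected = rate × 400 (the enrolment target in section 1.5):
- 1%: 0.01 × 400 = 4, leaving 396
- 3%: 0.03 × 400 = 12, leaving 388
- 5%: 0.05 × 400 = 20, leaving 380

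**Step 3. Does power suffer if all of them are lost?** Start with the plan's own figure. Section 1.5 gives 300 participants for 85% power, a medium effect and a p-value of 0.05, but names no test. One reading reproduces it: a chi-square test of appeal within each of three race/ethnicity groups, with w = 0.30 (the conventional medium value, an assumption), one degree of freedom and noncentrality λ = n × w².
- n = 100 per group: λ = 100 × 0.09 = 9, power 0.851; 3 × 100 = 300, which matches.

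On the same reading, with equal groups (also an assumption):

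| Allocated | Per group | Power |
|---|---|---|
| 400 | 133 | 0.933 |
| 396 | 132 | 0.932 |
| 388 | 129.3 | 0.927 |
| 380 | 126.7 | 0.922 |
| 300 | 100 | 0.851 |

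The total falls to 300 only if 1 − 300/400 = 25% of students are lost.

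**Step 4. Is the comparison between appeals biased?** A student lost for want of a stratum is lost before any appeal is assigned. The loss cannot depend on the arm, so the students who are allocated remain a fair comparison. Only the population to which the result applies could narrow.

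**Step 5. What does omitting the stratum do?** Let σ² be the variance of the outcome within strata, τ² the variance between stratum means, and n the number per arm. If the arms are balanced within strata, the difference in means has variance of about 2σ²/n, while an analysis without the stratum estimates about 2(σ² + τ²)/n. Its standard error is too large by √(1 + τ²/σ²), and the test is conservative to that extent. If allocation within sex is not forced to balance, including the stratum still removes chance imbalance. The documents do not give τ², so the gain cannot be sized.

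**The case against.** The strongest case on the other side is that this is silence, not error. Section 1.3 A says participants are randomised to one appeal or the other, with no exception, and section 4.4 B says students will view one condition. A default branch, an other-or-blank branch or a required item would all be compatible with the text. The measures themselves sit in an appendix that is not in the available text.

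That argument defeats three stronger readings that a reader might infer:
- *Such a student has no route to either appeal.* No section lists the strata or describes the survey flow, so nobody can be shown to fall outside them.
- *The right to skip and the stratification rule contradict each other.* A catch-all stratum satisfies both. Section 4.7 E is also narrower than a right to skip everything: it is addressed to participants who become uncomfortable, and the age check and consent box still gate entry.
- *Unallocated students would count towards accrual.* Section 4.3 A counts complete subjects and expects 500 screened for 400. It does not say that a student who saw no appeal is complete.

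It can also be said that a third level with about 4 students adds little to a model, and that baseline intentions, if used as a covariate, may already absorb much of any sex difference. Both points are fair, but section 6.1 does not say that baseline is used.

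What remains is that each innocent explanation still needs a sentence in the protocol. A required item would also have to be reconciled with 4.7 E. The omission of the randomisation factor from the analysis does not depend on how the survey was built.

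**Conclusion.** The concern holds as an incomplete allocation rule and an analysis that does not carry the randomisation factor. It does not hold as a demonstrated loss of students. The number affected is unknown; 4 to 20 of 400 rests on an assumed 1% to 5%. Planned power is safe: 0.92 to 0.93 per race/ethnicity group over that range, given w = 0.30, equal groups and the within-group reading of section 1.5. Between-arm validity is not threatened. Taken alone, the undefined strata are close to a missing detail. The more substantive change is to include sex, as randomised, in the emotional-versus-rational comparison.

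**What to change.** **Section 1.3 A.** Name the strata as male, female, and other or not answered. Give each its own 1:1 evenly balanced Qualtrics randomiser. Alternatively, send blank and other answers to an unstratified fallback randomiser. Either way, every consented student who reaches that point is allocated and section 4.7 E stays as it is. If the survey already does this, only the sentence is needed.

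**Section 6.1.** State that the emotional-versus-rational comparison includes the randomisation stratum as a factor. Code blank and other answers as their own level, so that allocated students are not dropped from the model because sex is missing.

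**Cost.** One extra survey branch at most, and two or three sentences. The third stratum will be very small, with a possible imbalance of a student or two. The factor uses one degree of freedom with two levels or two with three. In a model with 2 appeals × 3 race/ethnicity groups = 6 cells and 400 students, residual degrees of freedom go from 400 − 6 = 394 to 392 at most, which is negligible.

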1.4 Preliminary Data

N/A

1.5 Sample Size Justification

Prior research has demonstrated an effect size of $w=0.38$ (medium effect) between an emotional and rational appeal, thus we expect a medium effect size (Studts et al., 2010). In order to compare the effect of the two conditions (emotional/rational) by race/ethnicity (White, African-American, Latinx considered as the primary groups represented, recognizing there will be others) we will need 300 participants to have 85% power to detect a medium effect with a p-value of 0.05. To be conservative and ensure we have a large enough sample of each race/ethnicity group, we will seek to enroll 400 students.

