1.0 Research Design

1.1 Purpose/Specific Aims

The current study seeks to understand factors that influence college students' likelihood of participating in the National Marrow Donor Program (NMDP)/Be the Match for bone marrow and stem cell donations. The secondary aim is to compare emotional and rational approaches to encouraging participation in the registry and how these approaches may impact intentions to participate in the NMDP.

A. Objectives

1. The study will describe the role of demographic, personality, and psychosocial factors in attitudes towards participating in the National Marrow Donor Program.
2. Two strategies for increasing motivation (emotional appeal or factual data on racial/ethnic disparities in representation on the registry) for enrollment will be tested.
3. Strategies for enrollment will be compared by Race and Ethnicity to understand the best approaches to recruiting diverse students into the registry program.

B. Hypotheses / Research Question(s)

Approximately 12,000 patients need a bone marrow transplant each year to treat their cancer or other hematologic condition, but only about 30% of these patients find matches within their families (National Marrow Donor Program, 2013). The NMDP maintains a list of potential donors through the "Be the Match" organization which often runs donor drives on college campuses. Bone marrow donors are matched on genetic similarities, making race and ethnicity an important component in finding a match between a patient and a potential donor. Donors registered with Be the Match are 67% White, making it more difficult for individuals of color to find good matches, which may delay transplants and ultimately impact survival and the success of transplants. Thus, diversity is an important component of enrolling potential donors in the transplant registry. Because the student body of Rutgers Camden is diverse and within the age range targeted to join the NMDP, understanding psychological factors that contribute to participation and the most effective strategies to cultivate enrollment intentions is an important step towards enhancing the diversity of the donor registry and improving health outcomes for patients of color.

1. It is hypothesized that students who report high levels of altruism will be more likely to report an intention to enroll in the stem cell transplant registry.

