2. It is hypothesized that students who report high levels of knowledge about stem cell transplants will be more likely to report an intention to enroll in the stem cell transplant registry.
3. It is hypothesized that high altruistic students will be more likely to enroll when presented with an emotional appeal.
4. It is hypothesized that high knowledge students will be more likely to enroll when presented with a factual appeal.
5. It is hypothesized that the rational appeal which focuses on health disparities will result in a higher likelihood of enrollment for students of color as compared to white students.
6. It is hypothesized that self-esteem will differ between individuals who do and do not indicate an intention to enroll in the registry.

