History of transplant/donation	Previous research by Narayanan et al., (2016) has included these 15 items to assess an individual's familiarity with the transplant and donation process.
Motivations to donate	Participants are asked to rank order 11 possible reasons that they may decide to register for the transplant registry (Bart et al., 2014). Participants will complete this measure before and after the Emotional/Rational condition presentation.
Attitudes towards bone marrow transplant	Participants will be asked 9 questions about their attitudes towards joining the bone marrow registry and donating stem cells at a later date. This measure has been used in previous research (Narayanan et al., 2016).
Ambivalence	The Simons Ambivalence Scale is a 7-item scale developed to assess feelings about solid organ donation(Gardner, 1987). The measure has been modified for stem cell donor participation (Fingerut et al., 2020) and 4 of the 7 items will be used in the current study.

B. Dependent Variables or Outcome Measures

The primary dependent variable is intentions to register in the bone marrow transplant registry.

Secondary Dependent Variables: Participants will be asked about how factual and how emotional they perceived the appeal they received is to determine if the manipulation worked. We will also ask about their current mood again.

Construct/Measure	Description
Intentions to register	Participants will be asked 2 questions about whether they will register and the rate the likelihood of registering. They will be asked these questions before and after the experimental manipulation.
Manipulation Check	Participants will be asked to rate how emotional and how factual the appeal they received was on a 1-7 scale.
Mood	Participant mood will be assessed pre/post survey, asking participants to rate their current mood on a 1-10 scale.

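### Does section 1.5 overstate its 85% power for the race/ethnicity comparison by leaving the test and the size of a medium effect unspecified?

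*Combined protocol and SAP*

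**What the plan says.** Section 1.5 starts from a prior study's w = 0.38 for the overall contrast of appeals and continues: "medium effect) between an emotional and rational appeal, thus we expect a medium effect size". It then turns to the appeals by race/ethnicity, with "White, African-American, Latinx considered as the primary groups represented, recognizing there will be others", and states that "we will need 300 participants to have 85% power to detect a medium effect with a p-value of 0.05". The target is then raised: "To be conservative and ensure we have a large enough sample of each race/ethnicity group, we will seek to enroll 400 students".

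Two parts of section 1.1 depend on race/ethnicity. Objective 3 reads "Strategies for enrollment will be compared by Race and Ethnicity to understand the best approaches to recruiting diverse students into the registry program". Hypothesis 5 expects the rational appeal to produce a "higher likelihood of enrollment for students of color as compared to white students". Section 1.6 places race/ethnicity among the secondary predictors: "Additionally, demographic factors (race/ethnicity, sex, age), Altruism, Self-Esteem and Knowledge will be tested as secondary independent variables". The primary outcome, intention to register, has two items: "Participants will be asked 2 questions about whether they will register and the rate the likelihood of registering". Both are asked before and after the appeal. Section 6.1 names ANOVA and linear regression and gives no model terms.

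**The concern.** Objective 3 asks whether the better appeal depends on race/ethnicity, which is a difference between groups. The w = 0.38 in section 1.5 describes the overall contrast of appeals. The arithmetic that best matches 300 and 85% is a test inside one group. Power to see an effect within a group is not power to see that the effect differs between groups, and the second is usually lower.

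Section 1.5 also expects students outside the three named groups, so 300 would not yield 100 in each, and no expected shares are given. The risk is one of interpretation: a null race/ethnicity result might be reported as a negative finding with 85% power when that depends on assumptions the plan does not state.

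**Working it through.** **Inputs from the plan.** Two-arm design; alpha 0.05; 85% power; N = 300, raised to 400; three primary groups; w = 0.38 for the overall contrast.

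**Assumptions.** Two-sided tests; 1:1 allocation; equal groups unless stated; w = 0.30 as the conventional medium value; f = 0.25 as the conventional medium value for ANOVA.

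**1. The plan's own figure.** For a 1-df chi-square test the noncentrality is n·w². With n = 100 and w = 0.30 this is 100 × 0.09 = 9.0, and power is 85.1%. Three such groups make 3 × 100 = 300, so the figure reproduces. At w = 0.38, 63 per group suffice (85.5%), or 3 × 63 = 189.

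**2. Room for other groups at N = 400.** At w = 0.30 a group keeps 85% if it has 100 students (100/400 = 25%). At w = 0.38 it needs 63 (63/400 = 15.75%). If other groups take an assumed 10%, 20% or 25%, three equal main groups hold 120, 107 or 100 students. Within-group power is then 91%, 87% or 85% at w = 0.30, and 97-99% at w = 0.38.

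**3. Difference between groups: 2-df interaction.** A standardized appeal effect D corresponds to w through D = 2w to 2w/√(1−w²). This gives 0.60-0.63 for w = 0.30 and 0.76-0.82 for w = 0.38. The noncentrality is λ = Σ(n_g/4)(d_g − d̄)².

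With three equal groups and effect D in one only, λ = (N/12)(2/3)D². At D = 0.60 this is 25 × 0.667 × 0.36 = 6.0 for N = 300 and 8.0 for N = 400. If the other groups have D/2, λ is multiplied by 1/4. If they have −D/2, it is multiplied by 9/4.

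| Appeal effect in the three groups | w = 0.30, N = 300 | w = 0.30, N = 400 | w = 0.38, N = 300 | w = 0.38, N = 400 |
|---|---|---|---|---|
| D, 0, 0 | 58-62% | 71-76% | 80-86% | 90-94% |
| D, D/2, D/2 | 18-19% | 22-24% | 26-30% | 34-39% |
| D, −D/2, −D/2 | 92-94% | 97-98% | 99% or more | over 99% |

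If the medium effect is the interaction itself at f = 0.25, λ = 300 × 0.0625 = 18.75 and power is 98% at N = 300.

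**4. White students against students of color, N = 400.** Take the effect on one side only and an assumed White share of 20% to 50%. Power rises from 67-71% to 85-88% at w = 0.30, and from 86-91% to 97-98% at w = 0.38.

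**5. Hypothesis 5 as worded.** It can be read as a comparison inside the rational arm, about 200 students. The difference detectable with 85% power is 2.996·√(1/n₁ + 1/n₂), where 2.996 = 1.960 + 1.036.
- White share 20% (40 against 160): 0.53 SD.
- White share 50% (100 against 100): 0.42 SD.

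For a difference between appeal effects, using both arms, the formula is 2.996·√(2/n₁ + 2/n₂) with the same per-cell numbers. It gives 0.75 SD and 0.60 SD.

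**6. Overall comparison of appeals.** At w = 0.30 and N = 300 the noncentrality is 27 and power exceeds 99.9%.

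**The case for a change.** The strongest case for a change is that section 1.5 holds the only power statement and attaches it to race/ethnicity, and a reader cannot tell what it covers. Between-group power runs from under 20% to over 99% across the patterns above. The within-group match answers a different question from Objective 3. The f = 0.25 reading does not explain 300 either, since 178 students would suffice for it. Two sentences in sections 1.5 and 6.1 would settle the matter at no cost in participants.

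Part of this stands: the test, the outcome item, the numeric effect and the expected group shares are not written down, and stating them would be good practice.

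The step from there to a power problem does not follow. The low figures come from the pattern in which the appeal works half as well in the other two groups, which nothing in the documents predicts. Section 1.2 reports emotional appeals as more effective in general, and Hypothesis 5 expects the disparity-focused appeal to do better among students of color. An effect that vanishes or reverses in some groups is at least as compatible with that. Nor is the effect size wholly absent, since w = 0.38 is given and labelled medium. A single detectable difference for White students against students of color would rest on a White share that the documents do not give. It would also commit the team to the more demanding reading of Hypothesis 5.

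**Conclusion.** This is a gap in documentation that analysts can fill sensibly, and no change to the plan follows. The stated 300 and 85% reproduce exactly under one plain reading and are exceeded under another, so no stated figure is shown to be missed. The plan already answers the point about smaller groups by enrolling 400.

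At 400 and w = 0.38, the plan's only number, power exceeds 85% within any group of at least 63 students. It also does so for the three-group interaction when the effect is confined to one group (90-94%), and for White students against students of color (86-98%). The exception is the half-effect pattern, at 34-39%. At an assumed w = 0.30 the interaction has 71-76% or 97-98%, depending on whether the effect is absent or reversed in the other groups.

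Race/ethnicity is a secondary predictor, and the primary comparison of appeals is not in doubt. A condition-by-race/ethnicity term fits naturally in the ANOVA or regression of section 6.1. Reported with its confidence interval, it would keep a null result from being over-read.

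These figures assume two-sided tests, 1:1 allocation, equal main groups or the stated White shares, and no adjustment for baseline intention. Such adjustment would raise power.
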